### **8.1.1      *Rescue Therapy***

During the study, subjects with a worsening of EGE symptoms requiring rescue therapy (defined as a severe EGE flare; refer to [Section 6.4.2.10](#)) may be eligible to continue to participate in the study according to protocol requirements. Rescue therapy includes EGE standard of care pharmacotherapy (including but not limited to systemic corticosteroid therapy over the baseline dose) and/or dietary modification (eg, food elimination diet). Note that as part of study eligibility criteria and as described below in Section 8.2, in general, use of these treatment modalities is prohibited unless documented as required therapy for an EGE flare following IP administration.

Concomitant used of systemic corticosteroid therapy with or under the baseline dose (up to 10 mg/day of prednisone) is not considered as rescue therapy.

## **8.2              *Prohibited Concomitant Medications and Procedures***

Concomitant medications and procedures that are prohibited for a specific time period prior to the first Screening Visit and throughout the duration of the study include the following (the timeframe before the first Screening Visit is specified below); however, exceptions will occur in the event of a severe EGE flare requiring rescue therapy and in such cases, subjects may continue participation with concomitant rescue therapy (eg, systemic corticosteroids over 10 mg/day as prednisone). In such cases, a subject may be eligible to participate in the OLE Phase ([Section 3.1.6](#)):

- Subjects may not use systemic immunosuppressive or immunomodulating drugs (including but not limited to, [REDACTED]  
[REDACTED]  $\alpha 4\beta 7$  integrin inhibitor antibodies, or any other monoclonal antibodies, methotrexate, cyclosporine, azathioprine, mercaptopurine, IFN $\alpha$ , TNF $\alpha$  inhibitors, etc) for at least 5 drug half-lives prior to the first Screening Visit and during the study (including the OLE Phase). Use of any of the aforementioned medications during study participation will result in the subject's permanent discontinuation from IP; exceptions are if corticosteroids are used as rescue therapy for an EGE flare (see [Section 8.1.1](#)) or if required for treatment of an AE upon discussion with the Medical Monitor.
- Subjects may not use systemic corticosteroid medication exceeding the baseline dose as background treatment (up to 10 mg/day of prednisone) from the first Screening Visit through the Induction Phase and the Maintenance Phase. Subjects who have received corticosteroid therapy for EGE or another indication must have decreased the dose under 10 mg/day of prednisone and kept the systemic corticosteroid dose at that level within 4 weeks of the first Screening Visit. However, if a subject experiences a severe EGE flare during study participation following IP administration, the subject may continue participating in the Induction Phase and the Maintenance Phase with concomitant corticosteroid rescue therapy according to protocol pre-specified criteria (see [Section 6.4.2.10](#)).
- Subjects may not use high potency topical corticosteroids (eg, augmented betamethasone dipropionate, clobetasol propionate, etc) for dermatologic conditions within 8 weeks prior to the first Screening Visit through the Induction Phase and the Maintenance Phase.
- If subjects have not received PPIs, leukotriene receptor antagonists (eg, montelukast) or mast cell stabilizers (eg, cromolyn sodium) for the indication of EGE prior to the first Screening Visit, the subjects may not initiate these medications for the indication of EGE after 4 weeks prior to the first Screening Visit through the Induction Phase and the Maintenance Phase.
- Subjects may not receive oral or sublingual immunotherapy (treatment to desensitize to an allergen) within 6 months prior to the first Screening Visit through the end of the study (including the OLE Phase).
- Subjects may not receive live (including attenuated) vaccines within 1 month prior to the first Screening Visit through the end of the study (including the OLE Phase).
- Concurrent treatment with another IP (including an investigational treatment or investigational vaccine for COVID-19) is not allowed. Prospective subjects may not participate in a concurrent IP study or have received an IP within 5 drug half-lives prior to the first Screening Visit and through the end of the OLE study. For subjects who received an investigational COVID-19 vaccine as part of a clinical trial prior to the first Screening Visit, enrollment must be delayed until the biologic impact of the vaccine is stabilized, as determined by discussion between the investigator and the Clinical Trial Physician.

Refer to [Table 7](#) for a summary of the timing of restrictions on medication use as well as for certain procedures or dietary modifications required prior to study enrollment.

**Table 7: Medications, Diets, or Procedures Requiring Stable Dosing Regimens or Restricted Use Prior to Study Enrollment**

Medication, Diet or Procedure	Restriction Timeframe		
Medication (or procedure)	Subjects must not have received the following medication within the timeframe below before the first Screening Visit	Induction/Maintenance Phase	Open-label Long-term Extension (OLE) Phase
Systemic immunosuppressive or immunomodulating drugs	5 half-lives	Prohibited	Prohibited
Systemic corticosteroids exceeding the baseline dose (up to 10 mg/day of prednisone)	4 weeks	Prohibited	No restriction
High potency topical corticosteroids	8 weeks	Prohibited	No restriction
Initiation of proton pump inhibitors (PPIs), leukotriene receptor antagonists or mast cell stabilizers (for the indication of eosinophilic gastroenteritis [EGE])	4 weeks	Prohibited	No restriction
Oral or sublingual immunotherapy	6 months	Prohibited	Prohibited
Live (including attenuated) vaccines	1 month	Prohibited	Prohibited
Any other investigational product a	5 half-lives	Prohibited	Prohibited
Medication (or diet)	Subjects must be on stable dosing regimens within the timeframe below before the first Screening Visit	Induction/Maintenance Phase	OLE Phase
Diet (eg, food elimination diet)	4 weeks	Stable	No restriction
Systemic corticosteroid therapy with or under the baseline dose (up to 10 mg/day of prednisone)	4 weeks	Stable/Induction Phase Can be tapered or increased to the baseline dose /Maintenance Phase	No restriction, tapering is recommended
Inhaled corticosteroids, proton pump inhibitors (PPIs), leukotriene receptor antagonists, or mast cell stabilizers (for indications other than EGE)	4 weeks	Stable	No restriction
PPIs, leukotriene receptor antagonists, or mast cell stabilizers (for indications of EGE)	4 weeks	Stable	No restriction

**Table 7: Medications, Diets, or Procedures Requiring Stable Dosing Regimens or Restricted Use Prior to Study Enrollment**

Medication, Diet or Procedure	Restriction Timeframe		
Medication (or procedure)	Subjects must not have received the following medication within the timeframe below before the first Screening Visit	Induction/Maintenance Phase	Open-label Long-term Extension (OLE) Phase
Medium potency topical corticosteroids for dermatologic conditions	4 weeks	Stable	No restriction
Subcutaneous immunotherapy	3 months	Stable	No restriction

a For subjects who received an investigational Coronavirus disease 2019 (COVID-19) vaccine as part of a clinical trial prior to the first Screening Visit, enrollment must be delayed until the biologic impact of the vaccine is stabilized, as determined by discussion between the investigator and the Clinical Trial Physician.

### **8.3 Required Concomitant Medications and Procedures**

See inclusion criteria and exclusion criteria ([Section 4.2](#) and [Section 4.3](#)) for a description of corticosteroid treatment requirements and PPIs, leukotriene receptor antagonists, or mast cell stabilizer medication requirements and for study eligibility. See [Section 6.1](#) for Screening EGD requirements.

## **9 STATISTICAL CONSIDERATIONS**

### **9.1 Overview**

This is a Phase 3, multicenter, randomized, double-blind, placebo-controlled induction and maintenance study to assess the efficacy and safety of CC-93538 in adult and adolescent subjects with EGE. The study will incorporate a 16-week Induction Phase followed by a 32-week Maintenance Phase and an OLE Phase. Subjects will be randomized according to the following stratification factor: concomitant steroid use (yes or no). An independent DMC will be used to review the safety data regularly during the course of the study.

A primary database lock will be performed when all randomized subjects in this study have completed Week 48 of the Maintenance Phase or discontinued the study, including all Safety Follow-up Period data available to date. Analyses in the primary clinical study report (CSR) will be based on this database.

Analysis details not explained in the statistical section of the protocol will be provided in the Statistical Analysis Plan (SAP).

### **9.2 Study Population Definitions**

All study populations will be defined and documented prior to database lock. The following analysis populations will be used in the statistical analysis:

#### Intent-to-treat (ITT) Population

The ITT population will consist of all randomized subjects regardless of whether or not the subject received IP (CC-93538 or placebo).

The ITT population will be used as the primary population for all efficacy parameters. Subjects who prematurely withdraw from the trial for any reason and for whom an assessment is not performed for any reason will still be included in the ITT analyses. Subjects who received incorrect IP from what was randomized will be included in the treatment group according to the intended randomization. Subjects who were randomized with a misreported stratum will be analyzed according to their original (misreported) stratum.

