#### Induction Phase

Subjects experiencing a severe EGE flare and/or worsening of EGE symptoms (for 2 consecutive visits [4 weeks apart], described in [Section 6.4.2.10](#)) in the Induction Phase may continue to participate with concomitant rescue therapy as needed and will be eligible to enter the OLE Phase following completion of Week 16 of the Induction Phase. Subjects with a severe EGE flare in the Induction Phase will not qualify for entry into the Maintenance Phase.

If the gastric/duodenal eos count is required to determine the need for emergent rescue therapy during the Induction Phase, the results of the gastric/duodenal eos count will be disclosed as long as the investigator requires the result. The subject is to be discontinued from the study and will not be allowed to enter either the Maintenance Phase or the OLE Phase. All attempts should be made to complete the Induction Phase.

Subjects experiencing a mild to moderate EGE flare in the Induction Phase will continue to the Maintenance Phase of the study.

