## **7.3 Method of Treatment Assignment**

### **7.3.1 The Induction Phase and the Maintenance Phase**

Subjects enrolled in the Induction Phase will be centrally randomized on Day 1 after all screening and baseline assessments have been completed and the investigator has verified that the subject is eligible per the inclusion ([Section 4.2](#)) and exclusion criteria ([Section 4.3](#)). Subjects will be randomized 2:1 to receive active CC-93538 treatment (360 mg SC weekly for 16 weeks) or matching placebo for 16 weeks. Treatment assignment at baseline will be stratified by (with/without) concomitant use of corticosteroid treatment at baseline (up to 10 mg/day as the equivalent of prednisone) to ensure an equal balance in the treatment arms. Randomization will be performed through the Interactive Web Response System (IWRS) system.

Subjects enrolled in the Maintenance Phase will be centrally re-randomized on Week 16 (the completion of Induction Phase). Subjects who randomized to receive CC-93538 360 mg SC once weekly in the Induction Phase will be re-randomized 1:1 to receive active CC-93538 treatment (360 mg SC once weekly or 360 mg SC once every other week), and subjects who randomized to receive matching placebo in the Induction Phase will continue placebo. Re-randomization will also be performed through the IWRS system.

Treatment groups are described in [Section 7.2](#). The treatment each subject will receive will not be disclosed to the investigator, study center personnel, subject, Sponsor, or their representatives. The treatment codes will be held according to the IWRS. Further instructions will be provided in a separate IWRS manual.

The study blind should be maintained for persons responsible for the ongoing conduct of the study (after all subjects have completed the Week 48 assessments for endpoint analysis). Blinded persons may include but are not limited to: Clinical Research Physician (also referred to as Clinical Trial Physician), Clinical Research Scientist, Clinical Trial Manager, Study Statistician, Data Manager, Programmers, and Clinical Research Associates. For details of the emergency procedure for unblinding of individual subjects, see [Section 11.4](#).

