### **9.3 Sample Size and Power Considerations**

The sample size is based on two-sample t-test for the primary endpoint, changes in mean number of peak eos per hpf in GI biopsies from baseline to Week 16. The null hypothesis and the alternative hypothesis for the primary endpoint are as follows;

- Changes in mean number of peak eos from baseline at Week 16

Null hypothesis  $H_0: \mu_{CC-93538} = \mu_{Placebo}$

Alternative hypothesis  $H_a: \mu_{CC-93538} \neq \mu_{Placebo}$ ,

where  $\mu_{CC-93538}$  represents the true mean change value relative to CC-93538 and  $\mu_{Placebo}$  represents true mean change value relative to placebo.

Using this hypothesis, if the expected mean change in eos count in the active treatment group was -70, the expected mean change in eos count in the placebo group was 0, and the standard deviation (SD) was 70, the sample size necessary to achieve at least 80% power in a t-test at a significance level of 0.05 was calculated. Using a 2:1 ratio of active to placebo, 39 subjects are required. Assuming a Week 16 drop-out rate of approximately 10%, the goal is to enroll a total of 45 subjects.

The expected change from baseline in eos count in the active treatment group is based on the Phase 2 EoE study (Study RPC02-201); mean value at baseline for the CC-93538 360 mg treatment group of 139.4, and mean value at Week 16 of 31.3, with a percent change of approximately 80%. The baseline value in patients with EGE was assumed to be approximately 90 based on the results of studies of other drugs in patients with EGE (Dellon, 2020). Therefore, the expected change from baseline in eos in the active treatment group is assumed to be approximately 70. Change from baseline in eos count in the placebo group was assumed to be 0 based on the results of studies of other drugs (Dellon, 2020). With reference to the baseline GI eos count results of other drug studies of 52 (Dellon, 2020), the results of Study RPC02-201 in the CC-93538 360 mg group of 90, and the results of Study RPC02-201 in the CC-93538 180 mg group of 71, SD was assumed to be 70, which is approximately the mean of those values.

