#### **9.6.1.2 Changes in Mean Number of Peak eos Count from Baseline to Week 16 (Induction Phase)**

The primary analysis will be conducted on the ITT population based on an analysis of covariance (ANCOVA) model with treatment group, concomitant steroid use (yes or no), and baseline eos count included in the model. The comparison between CC-93538 360 mg SC once weekly and placebo for change in number of peak eos count from baseline at Week 16 will be made using the difference in least squares mean (LSM) at a 5% 2-sided significance level. Point estimates for the mean difference between the two treatment groups using the LS mean changes and corresponding 95% Wald CI will be reported. In addition, LSMs (standard error [SE]), arithmetic means (SD), and arithmetic mean changes (SD) will be summarized by treatment group.

Missing data will be handled using a multiple imputation (MI) approach under a missing at random (MAR) assumption.

Sensitivity analyses will be performed to support the primary analysis and provide additional insights to understand the treatment effect. For the primary estimand analysis, robustness due to missing data MI under MAR assumption will be explored using tipping point analysis ([Yan, 2009](#); [Campbell, 2011](#); [Yuan, 2014](#)). In considering the ICEs of study interest (ie, ICE number 2, use of rescue therapy/prohibited medication, and ICE number 3, treatment discontinuation followed by use of rescue therapy/prohibited medication), an analysis using the hypothetical estimand strategy for change in eos count at Week 16 will be conducted.

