### **9.6.3 Analysis of Secondary Efficacy Endpoints**

#### **9.6.3.1 Analyses Methods**

##### Continuous variables:

- Changes in mean number of peak eos count per hpf from baseline to Week 48
- Changes from baseline in each of 5 domain scores of the Izumo Scale (Weeks 14, 16, 32, and 48)
- Changes from baseline in total score of EGID Severity Score (Weeks 16, 32, and 48)
- Percent changes in mean number of peak eos per hpf in GI biopsies from baseline (Weeks 16 and 48)
- The time until concomitant corticosteroid treatment to zero (and continued by Week 48) (from Week 16 through Week 48)

The analysis for continuous variables of the secondary endpoints will be conducted on the ITT population using the ANCOVA model with treatment group (CC-93538 360 mg SC once weekly, CC-93538 360 mg SC once every other week, and placebo), prior steroid use (yes or no), and baseline values included in the model. Point estimates for the mean difference between the treatment groups using the LS mean changes and corresponding 95% Wald CI will be reported. The transition from the Maintenance Phase to the OLE Phase will be treated as ICE. Missing data and ICEs will be handled via the same strategy as for the primary analysis.

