##### Dichotomous variables:

- The proportion of responders defined as subjects who achieve both clinical and histologic response (Weeks 16 and 48):
  - Clinical response is defined as the proportion of subjects achieve  $< 4/15$  in all Symptoms of Interest (Gastric Pain Symptoms domain, Stomach Heaviness Symptoms domain, and Diarrhea Symptoms domain) of the Izumo Scale
  - Histologic response is defined as a  $> 75\%$  reduction of peak gastric and/or duodenal eos count from baseline

- The proportion of subjects achieving eosinophilic histologic response defined as a > 75% reduction of peak gastric and/or duodenal eos count from baseline (Weeks 16 and 48)
- The proportion of subjects who achieve < 4/15 in all Symptoms of Interest (Gastric Pain Symptoms domain, Stomach Heaviness Symptoms domain, and Diarrhea Symptoms domain) of the Izumo Scale (Weeks 14 to 16, 30 to 32, and 46 to 48)
- The proportion of subjects for whom the dose of concomitant steroids is reduced to zero (Weeks 24, 32, 40, and 48)

The analysis of the response endpoint will be conducted on the ITT population using the Cochran-Mantel-Haenszel (CMH) test stratified by concomitant corticosteroid treatment at baseline (yes or no). In case the Mantel-Fleiss criterion is not met, the Fisher's exact test will be performed instead of the CMH test. For treatment comparison between a CC-93538 dose and placebo, the 2-sided 95% stratified Newcombe CI ([Yan, 2010](#)) for the difference in proportions using the CMH weights will be provided. Missing data and any observed data after rescue therapy/prohibited medication which may impact the efficacy assessment will be set as non-responders.

Time to event data:

- The time to event of EGE flare (Through Week 48)
- The time to event of use of rescue therapy (Through Week 48)
- The time until concomitant corticosteroid use to zero (From Week 16 through Week 48)

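### Week 48 arm membership is undefined for CC-93538 subjects who are never re-randomised, while equivalent placebo subjects stay in placebo

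*Combined protocol and SAP*

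**What the plan says.** Section 9.2 defines the ITT population as all randomised subjects, keeps those who withdraw early or miss an assessment, and adds: "The ITT population will be used as the primary population for all efficacy parameters".

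The regimen is assigned later, and to fewer people. Section 7.3.1: "Subjects enrolled in the Maintenance Phase will be centrally re-randomized on Week 16 (the completion of Induction Phase". Section 6.2 restricts re-randomisation to eligible subjects. Sections 3.1.6, 6.4.2.11 and 11.1 list what bars entry to Maintenance: severe flare, worsening over two visits, other significant findings, permanent discontinuation of study drug, and certain prohibited changes. For example: "Subjects with a severe EGE flare in the Induction Phase will not qualify for entry into the Maintenance Phase". The same rules apply to both arms.

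For continuous secondary endpoints, Section 9.6.3.1 fits an ANCOVA on the ITT population with "treatment group (CC-93538 360 mg SC once weekly, CC-93538 360 mg SC once every other week, and placebo" as the treatment factor. Response endpoints are also analysed on ITT, with confidence intervals for a CC-93538 dose against placebo, under this rule: "Missing data and any observed data after rescue therapy/prohibited medication which may impact the efficacy assessment will be set as non-responders". Time-to-event endpoints include "The time to event of use of rescue therapy (Through Week 48" among their entries.

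No section says where a CC-93538 subject without a regimen is counted. Section 9.6.3.1 treats a move from Maintenance to the open-label extension as an intercurrent event but does not mention a move there from Induction. Section 9.1 leaves further detail to an SAP, and no SAP text is in the file.

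**The concern.** The analysis set is fixed at Day 1 but two of its three treatment labels exist only from Week 16. A placebo subject who fails or leaves in Induction still belongs to placebo at Week 48. A CC-93538 subject with the same history belongs to neither regimen. The likely ad hoc placements give an uneven comparison, and they push the results in different directions.

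Two secondary objectives rest on these contrasts: efficacy and persistence against placebo at 48 weeks, and persistence under less frequent dosing. The composite clinical and histologic response is a key secondary endpoint at Week 48 (Table 2). Sections 3.1.4 and 7.2.3 say the open-label regimen may be revised once results are available, so weekly versus every-other-week may inform a real decision. Choosing the placement after the data are seen would be choosing which contrast is flattered.

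**Working it through.** **The plan's own figure.** The sample size concerns the primary Week 16 endpoint: difference 70, SD 70, 2:1 allocation, "80% power in a t-test at a significance level of 0.05 was calculated" (Section 9.3), with a "difference in least squares mean (LSM) at a 5% 2-sided significance level" (Section 9.6.1.2). Noncentral-t power is 78.5% for 12 + 24 = 36 subjects and 81.8% for 13 + 26 = 39, so the stated 39 reproduces. Allowing for 10% drop-out, 39/0.9 = 43.3, rounded up to 44; the next multiple of three is the stated 45. Section 3.1.2 gives arms of about 30 and 15.

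**Inputs for Week 48.** Let *b* be the share not re-randomised, equal in both Day 1 arms, and *r* the response among entrants, equal in all arms (no drug effect). Non-entrants count as non-responders. The documents give neither *b* nor *r*; I assume *b* = 10% to 30% and *r* = 40%. The only related figure is the drop-out of about 10% by Week 16, which is not the same quantity.

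**Formulas.**
- Placebo, all 15 kept: (1 − *b*)*r*.
- (a) CC-93538 non-entrants omitted: each regimen has rate *r*, so the bias against placebo is *r* − (1 − *b*)*r* = *br*.
- (b) Non-entrants kept under the Day 1 weekly label: weekly = 15(1 − *b*)*r* / [15(1 − *b*) + 30*b*]; every-other-week = *r*.

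| *b* | CC-93538 without a regimen (of 30) | Placebo rate | (a) Regimen minus placebo | (b) Weekly rate | (b) Every-other-week minus weekly |
|---|---|---|---|---|---|
| 10% | 3 | 36% | +4 points | 5.4/16.5 = 32.7% | +7.3 points |
| 20% | 6 | 32% | +8 points | 4.8/18 = 26.7% | +13.3 points |
| 30% | 9 | 28% | +12 points | 4.2/19.5 = 21.5% | +18.5 points |

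For *r* from 30% to 70%, *br* runs from 3 to 21 points. In simulation of (a) with *r* = 50% (6,000 runs per cell, two-proportion z-test standing in for CMH), a nominal 5% test rejected about 6.5%, 9% and 13% of the time for *b* = 10%, 20% and 30%.

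**Continuous endpoints.** The non-responder rule does not apply. Under (a) the bias is *b* times the difference between non-entrants and entrants: zero if they do not differ. If non-entrants are 1 SD (70 eos/hpf) worse, the simulated bias is about 7, 14 and 20 eos/hpf, with rejection rates of 5.6%, 7.2% and 9.5% (unadjusted t-test, ignoring the planned imputation).

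**Time to rescue, only if drawn by regimen with non-entrants omitted.** Rescue in Induction means a severe flare, which bars re-randomisation, so a regimen arm could have no event before Week 16. With a constant equal hazard and Week 16 risk *p*, Week 48 rates are 1 − (1 − *p*)³ for placebo and 1 − (1 − *p*)² for a regimen. At *p* = 20% that is 49% against 36%.

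**Symmetric alternatives.** Pooled by Day 1 arm, both sides have rate (1 − *b*)*r*, so the no-effect bias is zero. With Maintenance entrants on both sides, each has rate *r*; simulated type I error was 4.4% to 5.8%. With weight 2 for re-randomised subjects and 1 for non-entrants, at *b* = 20%: (2 × 12 × 0.4)/(2 × 12 + 6) = 9.6/30 = 32%, equal to placebo.

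**The case against.** The strongest reply is that this is a gap in specification, not a biased analysis. The text does not say that non-entrants are dropped or kept as weekly. Symmetric treatments exist. Table 5, footnote t, sends all Maintenance subjects through re-randomisation in the IWRS, placebo included, so one could read the Week 48 set as entrants in every arm. Sections 9.4 and 9.7 already plan a total CC-93538 group for baseline and safety summaries. Section 9.1 defers detail to an SAP, and Section 9.2 promises that populations will be documented before database lock.

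Much of this stands. A reader might infer that the Week 48 comparison is biased as planned, or that omission and the Day 1 label are the only choices; the documents support neither, because placement is left open. A reader might also infer that the regimen arms are protected from rescue events before Week 16. The time-to-event text compares a treatment group with placebo and names no regimen, so that follows only if the curves are drawn by regimen.

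The size is also uncertain and may be modest. At 10% not re-randomised and 40% response, the bias under omission is 4 points. The standard error of the difference is √(0.4 × 0.6/13.5 + 0.36 × 0.64/15) ≈ 18 points.

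What does not stand is that the text already resolves the matter. An entrants-only set contradicts Section 9.2, which keeps early leavers for all efficacy parameters. Footnote t belongs to the Maintenance schedule and does not reach non-entrants. The total CC-93538 group is not specified for efficacy.

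**Conclusion.** The point holds as a defect of definition with predictable consequences. The protocol fixes the Week 48 set at Day 1, compares arms that exist only from Week 16, and leaves CC-93538 non-entrants without an arm while retaining their placebo counterparts.

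On responder endpoints, with no drug effect, omission favours both regimens over placebo by 4 to 12 points, and the Day 1 label favours every-other-week over weekly by 7.3 to 18.5 points. Both ranges assume equal shares of 10% to 30% not re-randomised and 40% response among entrants. Continuous endpoints are affected only if non-entrants differ from entrants, which is likely but not certain. Time-to-event endpoints are affected only if analysed by regimen.

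A reader should not carry this over to the primary result: the Week 16 comparison uses the two Day 1 arms and is unaffected. All Week 48 p-values are nominal, although that does not protect the estimates and intervals. Should-fix, with moderate confidence, since an SAP outside the file may already contain a rule; if so, it should be cited in the protocol.

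**What to change.** Amend Sections 9.2 and 9.6.3.1, and the SAP to match, before unblinding:

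1. **CC-93538 versus placebo at and through Week 48:** analyse by Day 1 randomised arm. Pool both regimens with all CC-93538 subjects not re-randomised, against all placebo subjects, with time-to-event measured from Day 1. State how a move from Induction to the open-label extension is handled.
2. **Weekly versus every-other-week:** re-randomised subjects only, with time-to-event measured from re-randomisation.
3. **Each regimen versus placebo:** pre-specify a rule that treats both sides alike. One option is Maintenance entrants on both sides, labelled as a post-randomisation subset; this removes the bias only under no drug effect, because the drug may change who enters. Another is inverse-probability weighting as a supportive analysis. It would need robust standard errors with roughly 12 to 15 subjects per regimen and a stated replacement for the CMH or Fisher test, the Newcombe interval and the log-rank test.

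The cost is wording and some programming, with no new data or subjects. The CC-93538 versus placebo estimates may look less favourable, and the contrasts of a single regimen with placebo become supportive only.
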